- Explore effects of weight, gender, BMI, or other potentially interacting factors on the responsiveness of the subjects to the experimental intervention.
- Optimize the recommended surgical implantation procedure, anatomical location, and peri- and post-operative care for VC-01.
- Further assess the effects of the host immune response to implanted VC-01 units.

Study Endpoints:

The study endpoints for each cohort are as follows:

Cohort 1

Primary Endpoint Measures:

- The percentage of viable graft cells at post-implant time points relative to pre-clinical models.
- The percentage of graft cells staining positive for markers of beta cells at post-implant time points relative to pre-clinical models.

Secondary Endpoint Measures:

- The qualitative assessment of the severity of the host immune response as rated at post-implant time points.
- The comprehensive safety profile of VC-01 implanted for up to six (6) months as measured by:
 - All reported adverse events (AEs).
 - The incidence of subjects requiring a premature explant due to safety issues.
 - The incidence of off-target growth as evidenced by implanted VC-01 units via lumen ultrasound measurements, or by histological examination of explants.
 - The incidence of immune sensitization defined by presence of donor anti-HLA (human leukocyte antigen) antibodies absent prior to implant.

Cohort 2

Primary Endpoint Measure:

• Change from baseline to Week 26 in C-peptide area under the curve from 0 to 4 hours (AUC_{0-4h}) following a Mixed Meal Tolerance Test (MMTT).

Secondary Endpoint Measures:

Safety and Tolerability

- Comprehensive profile of VC-01 combination product implanted for up to Month 12/Week 52 as measured by:
 - All reported AEs

- The incidence of immune sensitization defined by presence of donor anti-HLA antibodies absent prior to implant
- Implant tolerability assessments (e.g., fever, erythema, pain, tenderness, induration) post-implantation and at subsequent visits.
- The incidence of subjects requiring a premature explant due to safety, tolerability, or malfunction issues.

Efficacy

- Change from baseline to Weeks 8, 12, 16, 20, 26, 39, and 52 in C-peptide AUC_{0-2h} and change from baseline to Week 52 in C-peptide AUC_{0-4h} following an MMTT.
- Change from baseline to Weeks 16, 20, 26, 39 and 52 in average daily insulin dose in the 7 days preceding the clinic visit.
- Time to onset of biological response of C-peptide following MMTT.

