7.2. Mixed Meal Tolerance Test (MMTT) – Cohort 2 only

MMTTs are conducted after all other vital signs evaluations and laboratory tests have been collected. The MMTT test should only be started if the subject has been fasting for at least eight (8) hours. The MMTT may be rescheduled within the visit window if needed. All MMTT supplies will be provided by the Sponsor or designee. Basal exogenous insulin will be continued during the test, but any short-acting insulin will be withheld starting four hours prior to starting the test. Prior to initiating the MMTT, the subject's fasting glucose will be tested at the site and the value must be within 70-200 mg/dL to begin the MMTT. If the fasting glucose is not initially within range, the site may recheck levels while the subject is still at the clinic. If the fasting glucose remains outside of the allowed range, the subject must return to the site within the visit window and attempt the MMTT again.

An intravenous catheter can be placed in a patent vein in the subject's arm for the collection of blood samples. Insertion of the catheter should occur at least 30 minutes prior to any blood collections on the days MMTTs are performed. The subject should sit upright during the test. Slow walking is permitted, but vigorous exercise should be avoided.

Baseline, fasting blood samples are drawn for glucose and C-peptide within approximately five minutes prior to the start of the meal test. At time = 0, the subject drinks Boost® Hi-Protein (volume equal to 6 mL/kg body weight to a maximum of 360 mL). The entire drink must be ingested within 15 minutes.

For any visits requiring both an MMTT and an explant procedure, it is acceptable to perform the MMTT on a separate day up to 5 days prior to the explant procedure. Further details regarding MMTTs may be outlined in the study reference manual.

7.2.1. 4-Hour Mixed Meal Tolerance Test – Cohort 2 Only

The 4-hour MMTT is conducted only in Cohort 2 during Visit 2 (Week -4), Visit 11 (Week 26), and Visit 13 (Week 52 / Completion or ET). In addition to the time = 0 collection, samples for glucose and C-peptide are also collected at 30, 60, 90, 120, 180, and 240 minutes after the start of the Boost® meal test.

7.2.2. 2-Hour Mixed Meal Tolerance Test – Cohort 2 Only

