The 2-hour MMTT is conducted only in Cohort 2 during Visit 7 (Week 8), Visit 8 (Week 12), Visit 9 (Week 16), Visit 10 (Week 20), and Visit 12 (Week 39). In addition to the time = 0 collection, samples for glucose and C-peptide are also collected at 30, 60, 90, and 120 minutes after the start of the Boost® meal test.

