## 7.2 Baseline, Endpoint and Missing Value Definitions

#### 7.2.1 Baseline

Baseline will be defined as the last non-missing value prior to the start time of the surgical implantation procedure unless otherwise specified. For MMTTs in Cohort 2 subjects, the 4-hour MMTT performed during the Screening period is used for defining both the baseline 4-hour MMTT and the baseline 2-hour (using the first 2 hours of data) MMTT.

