## 7.2.6.2 Time to Onset of Biological Response of C-peptide Following MMTT

The biological response of C-peptide is defined as a value >0.2 ng/mL for the C-peptide measurement. For Cohort 2 subjects, time to onset of biological response of C-peptide will be calculated in two ways: the time to onset of biological response from implantation, and the time to biological response within each MMTT.

For the time to onset of biological response from implantation, the time unit will be 'days' and the time itself will be calculated as:

Time to onset of biological response of C-peptide (days) = (Date of first MMTT at which the subject achieved at least one C-peptide > 0.2 ng/mL) – (Date of surgical implantation procedure for the subject) + 1

For the time to onset of biological response within each MMTT, the time unit will be 'minutes' and the time itself will be calculated as:

Time to onset of biological response of C-peptide (minutes) = (Time during MMTT at which the subject first achieved a C-peptide > 0.2 ng/mL) – (Start time of Boost Hi-Protein drink for the MMTT for the subject)

For these time-to-event analyses, subjects who did not achieve biological response will be censored. That is, for the time to onset of biological response of C peptide from implantation, subjects who did not achieve at least one C-peptide > 0.2 ng/mL during any MMTT will be censored at the time they leave the study (complete the study, or withdrawal from the study).

For the time to onset of biological response within each MMTT, subjects who did not achieve at least one C-peptide within a 4-hour MMTT will be censored at 240 minutes. Subjects who did not achieve biological response of C-peptide during a 2-hour MMTT will be censored at 120 minutes.

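### Onset of C-peptide response from implantation is searched over 120 minutes at five visits and 240 minutes at two, so the onset curve can rise at Week 26 through test length

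*Protocol*

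**What the plan says.** Both documents list "Time to onset of biological response of C-peptide following MMTT" among the Cohort 2 secondary efficacy endpoints. SAP 7.2.6.2 defines it in two ways.

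- **From implantation, in days.** The event date is "Date of first MMTT at which the subject achieved at least one C-peptide" above 0.2 ng/mL. Any sample in the test counts. Subjects with no such value are censored when they leave the study.
- **Within each MMTT, in minutes.** Non-responders are censored at 240 or 120 minutes according to test length.

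The tests differ in length. For the 4-hour test (Protocol 7.2.1: Week -4, Week 26, Week 52/ET), besides time 0, "samples for glucose and C-peptide are also collected at 30, 60, 90, 120, 180, and 240 minutes". For the 2-hour test (Protocol 7.2.2: Weeks 8, 12, 16, 20 and 39), besides time 0, "samples for glucose and C-peptide are also collected at 30, 60, 90, and 120 minutes".

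The SAP allows for test length elsewhere. The screening 4-hour test also supplies "the baseline 2-hour (using the first 2 hours of data) MMTT" (SAP 7.2.1), and SAP 7.3.7.3 analyses AUC0-2h at Week 26, where the test lasts 4 hours. No such rule covers onset from implantation. SAP 7.3.7.3 specifies Kaplan-Meier curves and a logrank p-value without adjustment. Efficacy data from ET visits are mapped into the ordinary visit windows (SAP 7.2.6.7).

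**The concern.** The event is looked for harder at Weeks 26 and 52 than at the other visits: seven samples to 240 minutes against five to 120 minutes. A subject whose C-peptide passes 0.2 ng/mL only late in the meal test is invisible to every scheduled test before Week 26. Such subjects collect there and would appear as new onsets.

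Week 26 is an awkward place for this. It is the primary time point, and the cut for a possible descriptive report to support regulatory discussions (Protocol 10.3). It also falls at the end of the three to six months over which grafts are expected to mature (Protocol 5.1). A rise caused by longer sampling would look like the biology that the endpoint is meant to show.

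The percentage with a positive stimulated C-peptide has the same unequal window if it is tabulated by visit. ET tests, being 4-hour tests mapped to ordinary windows, could then also make test length differ between subjects at one analysis visit.

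**Working it through.** The readable text gives no sample size, event count or expected onset curve for this endpoint, so there is no planned figure to reproduce.

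**Step 1. The search window** (Protocol 7.2.1 and 7.2.2; target days from the Cohort 2 table in SAP 7.2.2)

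| Visit | Target day | Last sample | Samples |
|---|---|---|---|
| Week 8 | 57 | 120 min | 5 |
| Week 12 | 85 | 120 min | 5 |
| Week 16 | 113 | 120 min | 5 |
| Week 20 | 141 | 120 min | 5 |
| Week 26 | 183 | 240 min | 7 |
| Week 39 | 274 | 120 min | 5 |
| Week 52 | 365 | 240 min | 7 |

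**Step 2. Delay for a late-only crosser** (above 0.2 ng/mL only at 180 or 240 minutes)

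- Response present at Week 8: 183 - 57 = 126 days late.
- Week 12: 183 - 85 = 98 days.
- Week 16: 183 - 113 = 70 days.
- Week 20: 183 - 141 = 42 days.
- First present at Week 39: 365 - 274 = 91 days.

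These follow from the schedule alone. There are three exceptions: an ET visit before Week 26, which carries the 4-hour test; an unplanned MMTT (Protocol 6.15, length not stated); and a later sample mapped to a missing 120-minute point (SAP 7.2.6.1).

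**Step 3. Size of the Week 26 step.** Two inputs are assumed, because the documents give neither:

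- h, the chance of latent onset at each MMTT visit among those still without a response (5, 10 or 15%);
- q, the share of responders who cross late only (0 to 50%).

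Responses are taken to persist, and nobody leaves. Cumulative latent onset by the k-th visit is C(k) = 1 - (1 - h)^k, with Week 20 as k = 4 and Week 26 as k = 5.

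- Week 26 step, any-sample rule: [C(5) - C(4)] + q x C(4).
- Week 26 step, 0-120 minute rule: (1 - q) x [C(5) - C(4)].
- Difference: q x C(5).

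For h = 10%, C(4) = 1 - 0.9^4 = 34.4% and C(5) = 1 - 0.9^5 = 41.0%. At q = 20% the any-sample step is 6.6% + 0.2 x 34.4% = 13.4%, and the common-window step is 0.8 x 6.6% = 5.2%. The difference is 0.2 x 41.0% = 8.2% of subjects, or 3.3 of 40. Of these, 0.2 x 34.4% x 40 = 2.8 are delayed from earlier visits. The rest have late-only onset at Week 26 itself.

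| q (h = 10%) | Week 20 step | Week 26, any sample | Week 26, 0-120 min | Extra at Week 26, of 40 |
|---|---|---|---|---|
| 0% | 7.3% | 6.6% | 6.6% | 0 |
| 10% | 6.6% | 10.0% | 5.9% | 1.6 |
| 20% | 5.8% | 13.4% | 5.2% | 3.3 |
| 30% | 5.1% | 16.9% | 4.6% | 4.9 |
| 50% | 3.6% | 23.8% | 3.3% | 8.2 |

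At q = 20%, h = 5% gives 0.2 x 22.6% x 40 = 1.8, and h = 15% gives 0.2 x 55.6% x 40 = 4.5.

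**Step 4. What drives the late-only share.** I simulated single tests with an assumed curve A x [0.3 + 0.7 x g(t)], where g(t) = [(t/T) x exp(1 - t/T)]^2 and T is the peak time. A is lognormal with SD of log 0.6, and each sample has 10% noise. The gap is 4-hour minus 2-hour positivity, in percentage points.

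| Peak time T | Median A 0.22 | Median A 0.5 | Median A 1.0 |
|---|---|---|---|
| 180 min | about 8 | 3 | 0.3 |
| 210 min | about 14 | 5 | 0.6 |

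With peaks at 90 to 120 minutes the gap is below 1 point. The effect therefore belongs to responses that are both weak and late.

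**Step 5. Chance crossings.** With independent samples and a per-sample false-crossing chance p, the chance per test is 1 - (1 - p)^5 or 1 - (1 - p)^7. At an assumed p = 1% this is 4.9% against 6.8%. For a flat true level of 0.15 ng/mL it is 22% against 29% with SD 0.03, but 0.2% against 0.3% with SD 0.015. This part depends almost wholly on assay noise, which the documents do not state.

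**The case against.** The best defence is that only the unequal window is built into the design. A reader might infer that the onset curve must jump at Week 26, but the documents do not support that. A jump needs subjects who cross 0.2 ng/mL only after 120 minutes, and their share is not given. A late peak is harmless if the value has already passed 0.2 by 120 minutes. This objection stands.

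A reader might also infer an artificial fall in positivity at Week 39. First-event Kaplan-Meier onset cannot reverse, and the positivity endpoint names no weeks. The SAP's allowance for results at each time point where appropriate does not settle whether positivity will be tabulated by visit. This stands too.

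Parts of the plan soften the problem. The within-test analysis will show how many subjects first cross after 120 minutes at Weeks 26 and 52. AUC0-2h follows graft function on a common window from Week 16 to Week 39, so it would be too broad to say that maturation as a whole is confounded with test length. All data are listed. These outputs help a reader detect the artefact, but they do not remove it from the onset curve.

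Truncation also has a price. A subject above 0.2 ng/mL only at 180 minutes would be dated still later or censored, although that sample counts in the primary AUC0-4h. Which version should lead is therefore debatable.

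Finally, no hypotheses are tested, secondary p-values are descriptive, and all treatment groups share the schedule. The logrank test is affected mainly if the late-only share differs by number of units.

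**Conclusion.** The point holds in a limited form. The unequal search window is certain, and so are the delays of 42 to 126 days and 91 days for late-only crossers on scheduled tests, apart from the three exceptions in the working. The onset curve can step up at Week 26 for that reason; whether it will is unknown.

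The size rests on assumed values of h and q, on persistent responses and on no dropout. It runs from nothing at a zero late-only share (chance crossings aside) through about 2 to 4.5 of 40 subjects at a 20% share. It is small if responses are strong or peak by 120 minutes. By-visit positivity is affected only if it is tabulated that way.

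The harm is to the shape and median of a descriptive secondary curve, not to the primary AUC0-4h analysis. It is worth correcting because the remedy is cheap and uses data already collected.

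**What to change.** In SAP 7.2.6.2 and 7.3.7.3, add an analysis of onset from implantation restricted to the 0, 30, 60, 90 and 120 minute samples of every MMTT, including those at Week 26, Week 52 and ET. Apply the same restriction to positivity if it is shown by visit. Use this version to describe the time course across visits. Show the any-sample version, with its 4-hour window at Weeks 26 and 52, beside it, and state in a footnote that test length differs by visit.

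The cost is one extra table and curve, with no new samples or visits. Late-only crossers do not count as responders in the common-window version, so positivity at Weeks 26 and 52 may be slightly lower there. The change makes visits comparable. It does not correct the late dating of slow-peaking grafts, because the 2-hour tests never sample the period in which they would cross.

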GLP Good Laboratory Practice
GMP Good Manufacturing Practice

HbA1C Hemoglobin A1C

HBsAg Hepatitis B Surface Antigen

HCV Hepatitis C Virus

HDL High-Density Lipoprotein HE Hypoglycemic Event

hESC Human Embryonic Stem Cells

Hgb Hemoglobin

HLA Human Leukocyte Antigen
HIV Human Immunodeficiency Virus
HU Hypoglycemic Unawareness
IB Investigators Brochure

ICD Informed Consent Document

ID Identification

ICH International Conference on Harmonisation

IEQ Islet Equivalent IFU Instructions for Use

ISO International Organization for Standards

IUD Intrauterine Device

IUS Intrauterine hormone-releasing system

LAM Lactation amenorrhea method
LDH Lactate Dehydrogenase
LDL Low-Density Lipoprotein
LSM Least Squares Mean

MDRD Modification of Diet in Renal Disease
MedDRA Medical Dictionary for Regulatory Activities

MMTT Mixed Meal Tolerance Test
MRI Magnetic Resonance Imaging

NCI-CTCAE National Cancer Institute Common Terminology Criteria for Adverse Events

PE Physical Exam

PEC-01 Pancreatic Endoderm Cells
PI Principal Investigator
PPD Purified Protein Derivative
PRA Panel Reactive Antibody

PT Preferred Term
QC Quality Control
QTc Corrected QT Interval
RBC Red Blood Cell

SAE Serious Adverse Event
SAP Statistical Analysis Plan
SAS Safety Analysis Set
SE Standard Error

SHE Severe Hypoglycemic Event SMBG Self-Monitoring Blood Glucose

SOC System Organ Class

SOGCT Simplified Oral Glucose Challenge Test

SRM Study Reference Manual

SUSAR Suspected Unexpected Serious Adverse Reaction

T1DM Type 1 Diabetes Mellitus T2DM Type 2 Diabetes Mellitus

TB Tuberculosis

TEAE Treatment-Emergent Adverse Event

ULN Upper Limit Normal

VC-01 VC-01 Combination Product VLDL Very Low-Density Lipoprotein

WBC White Blood Cell

1. INTRODUCTION

1.1. Background Information and Scientific Rationale

Diabetes mellitus, a life-threatening disease growing at an alarming rate, has nearly quadrupled in prevalence between 1980 and 2014 (World Health Organization, 2016). In 2017, the number of adults worldwide with diabetes was estimated to be 425 million, or approximately 8.8% of the world's adult population. This number is projected to increase to 629 million globally by 2045. In the United States alone, over 30 million adults are estimated to be living with diabetes, with as many as 11 million additional, undiagnosed diabetics (International Diabetes Federation, 2017). Of the people diagnosed with diabetes, approximately 5% to 10% have type 1 diabetes mellitus (T1DM) and require exogenous insulin injections every day to survive (You & Henneberg, 2016).

The hallmark of diabetes is elevated blood glucose levels. Over time, this chronic hyperglycemia frequently results in both microvascular (e.g., retinopathy, neuropathy, nephropathy) and macrovascular (e.g., atherosclerosis, cardiac disease) complications, which severely increase morbidity and mortality, and diminish the patient's quality of life. Annual economic costs attributable to diabetes in the United States include \$176 billion for associated medical care and an additional \$69 million related to time lost from work. Medical care costs for people with diabetes are 2.3 times higher than for those without diabetes (McEwen, et al., 2018). Care for people with diagnosed diabetes accounts for greater than one in five health care dollars. (American Diabetes Association, 2013).

Diabetes patients who require insulin treatment include all patients with T1DM, which is caused by loss of insulin-producing pancreatic beta cell mass, and 20-30% of patients with type 2 diabetes mellitus (T2DM), who require insulin as adjunctive therapy. Each year, more than 17,900 children and adolescents younger than age 20 years are diagnosed with T1DM in the US alone (National Center for Chronic Disease Prevention and Health Promotion, 2017).

There is no known way to prevent or cure T1DM. Treatment involves frequent, painful, and cumbersome blood glucose monitoring followed by insulin injection. This standard of care can be woefully inadequate. Subjects employing frequent self-monitoring (finger stick) blood glucose monitoring are able to maintain strict glycemic control within the American Diabetes Association (ADA)-specified optimal range less than 30% of the time. (Bode, Schwartz, Stubbs, & Block, 2005) The most intensive forms of insulin therapy involve the use of Continuous Glucose Monitoring (CGM) systems, finger stick blood glucose measurement with portable meters, and implanted insulin pumps. Yet even these technologically-advanced systems require significant patient management and cannot control glycemia perfectly. More recently, complex systems combining CGM technology and insulin pumps have been developed to function as an artificial pancreas. While the approach shows some promise, blood glucose control still remains suboptimal relative to homeostatic euglycemia. Despite an increased use of technologies such as CGM and insulin pumps, only about 1 in 5 US patients with T1DM achieves optimal glycemic control (Foster, et al., 2019).

Importantly, insulin therapy also leads to periods of hypoglycemia. Patients using CGM may be hypoglycemic approximately 8% of each day, with a propensity for hypoglycemic events to occur

at night (Bode, Schwartz, Stubbs, & Block, 2005). In some cases, severe hypoglycemic events (SHE), e.g., those requiring the aid of another person to administer carbohydrates, glucagon, or other resuscitative assistance, can lead to seizures, unconsciousness, coma, and death. Importantly, a history of hypoglycemia can predispose patients to episodes of hypoglycemia unawareness (HU), which increases their risk of severe hypoglycemia and serious sequelae by at least 6-fold. (Seaquist, et al., 2013) Hypoglycemia, like hyperglycemia, should be avoided if possible.

Additional approaches to treatment of T1DM are being pursued including immunologic intervention in disease mechanisms, beta-cell regenerative and/or replacement therapies, and engineering solutions to enhanced glucose monitoring and insulin delivery. One such treatment with extensive development is the pancreatic islet transplant which may employ cells of either porcine or human origin. Although allogeneic islet cell transplantation has achieved insulin independence in some patients, the success rate from center to center has varied widely, and the duration of effect has been limited. Furthermore, islet transplant has two significant disadvantages. First, pancreatic islet transplantation requires chronic immunosuppression for the lifetime of the graft, which adds substantial risk including severe infection and potential progression of occult cancers. Second, its availability is limited by an insufficient supply of acceptable human pancreata as source material.

ViaCyte's VC-01 combination product has the potential to overcome the disadvantages represented by pancreatic islet transplant, yet still provide homeostatic control of blood glucose levels that is difficult to achieve with CGM and insulin pumps alone. Clinical trials involving VC-01 were initiated in 2014, but results thus far have indicated that a robust foreign body response (FBR) occurs relative to the device component of the product, thus preventing long-term, viable engraftment of the product (Henry, et al., 2018). ViaCyte has now developed new configurations of the device that have been tested in Cohort 1 in this protocol to evaluate whether the FBR has been properly mitigated to allow for functional product engraftment. This protocol now includes an Efficacy Cohort 2, to evaluate the potential of the product to generate a response at higher doses that are expected to be therapeutic. Based on strong evidence of safety and histological response at sub-therapeutic doses, it is now prudent and necessary to evaluate the product for clinical efficacy.

